#### **C.2.1.d Exclusion Criteria Treatment Phase**

To proceed to randomization and treatment phase of the trial the subjects must meet none of the following criteria after the screening phase:

- 1) Hypoalbuminemia defined as serum albumin <2.0g/dL
- 2) Renal dysfunction defined as serum creatinine >2.0mg/dL
- 3) Hepatic dysfunction defined as serum AST and/or ALT > 3 times upper limit of normal (approximately 120 IU/L however, will vary depending on age),
- 4) Significant anemia or polycythemia defined as hemoglobin >18gm/dL or hemoglobin <7gm/dL
- 5) Severely elevated serum BNP defined as BNP>300pg/ml

#### **C.2.1.e Subject Availability**

The estimated number of patients who meet trial eligibility criteria is approximately 150. Fontan patients are seen on an annual basis. Therefore, assuming a consent rate of 20%, the required 30 subjects can be enrolled within the two year timeframe.

#### **C.3. Recruitment and Eligibility Phases**

The Principal Investigator or designee at Children's Medical Center and the study coordinator will be responsible for case finding and subject recruitment.

For patients who meet inclusion criteria for the eligibility phase, the patient's cardiologist will be approached. Then potential study participants (if over 18 years of age) or the parent(s) or legal guardian of potential participants, will be approached about participation. At this time, a final determination about eligibility for the screening phase

of the study will be made, and eligible patients or parents will be asked to participate in the study.

A cardiologist experienced in the treatment of patients with Fontan circulation will be involved in obtaining consent. Data (demographic, eligibility criteria and informed consent status) will be recorded on a screening form for all patients with Fontan circulation, regardless of their inclusion in the study, for definition of the study population. The screening data will be obtained and stored in a confidential manner, in compliance with HIPAA requirements and local national regulations.

Each subject enrolled in the trial will be assigned a study identification (ID) number so that study information will be confidential. The link between subject name and ID number will be stored only in an encrypted password protected database at Children's Medical Center and will only be accessible to the PI, study investigators and research coordinators. Data that will be obtained on study participants includes demographic data and family history, information about their past and current medical care, echocardiographic imaging data, and information on adverse drug reactions and adverse events. The stress test data will be interpreted at Children's Medical Center by a study investigator and will contain the patient's name. The consent form will state this clearly. All study procedures are conducted in accordance with local and HIPAA requirements and regulations.

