## **A. SPECIFIC AIMS**

There is an unmet need for a better understanding of the effects of traditional heart failure medications in patients with Fontan circulation. It is now standard practice in developed nations for patients with a functional single ventricle (SV) circulation to undergo a three-stage surgical palliation. Survival to stage III palliation, the Fontan procedure, has greatly improved in recent decades. Despite complete physiologic palliation, Fontan subjects suffer from lower exercise capacity than their peers and have a poorer quality of life. The emphasis of SV care has evolved from preventing mortality to improving quality of life. The utility of traditional heart failure medications the SV population is not completely understood. Exercise testing is a frequently used measure of cardiovascular health, as it allows insight into cardiac and pulmonary responses to exercise and is a robust tool for predicting poorer cardiovascular outcomes in heart failure, including patients with Fontan circulation. The specific aims of this research are as follows.

**Primary Aim 1:** To compare the effect of carvedilol to that of placebo on peak exercise capacity.

*Rationale:* Peak exercise capacity is directly related to cardiovascular health and has been shown to be predictive of outcomes in patients with cardiovascular disease.

*Primary and Secondary Measures:* Peak volume of oxygen consumption indexed to patient weight (peak  $\text{VO}_2$ ) is the primary outcome measure. Secondary measures will include maximum watts performed, respiratory exchange ratio at peak exercise.

*Hypothesis:* Carvedilol will increase peak exercise capacity.

**Secondary Aim 1:** To compare the effect of carvedilol to that of placebo on chronotropy.

*Rationale:* Beta-blockers are sometimes avoided in Fontan patients because of a theoretical concern of worsening chronotropic incompetence. However, this has never been studied systematically.

*Measures:* Primary outcome measure is peak heart rate during exercise. Secondary measures will be heart rate reserve (heart rate at peak exercise minus baseline heart rate) and chronotropy reserve (peak heart rate minus baseline heart rate divided by the difference of predicted peak heart rate and baseline heart rate).

*Hypothesis:* Carvedilol will decrease peak heart rate

**Secondary Aim 2:** To compare the effect of carvedilol to that of placebo on submaximal exercise capacity

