## **C.5 Treatment Phase**

### **C.5.1 Masking of Treatment Group Assignment**

The primary endpoint and most of the secondary endpoints will be measured by the study investigator, who will be unaware of each subject's treatment group assignment. Randomization to treatment arm (carvedilol first versus placebo first) will be determined by Children's Medical Center investigational drug pharmacy.

No one else including subjects, their families, and primary care providers will be informed of the subject's treatment assignment.

The Data Safety and Monitoring Board (DSMB) will determine their preference for receipt of blinded or unblinded trial results prior to the interim look. No clinical investigators will review trial outcomes, by arm or in aggregate, until the end of the trial.

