### **C.6.3 Potential Benefits of the Proposed Research**

The possible benefits of participation in the proposed study to the subject are:

1. The subject's family, primary care provider, and cardiologist will receive extensive information regarding the subject's cardiac status.

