**Response to Bradycardia or Hypotension:**

1. Heart rate and/or blood pressure will be confirmed by two repeat measures after initial measurement with at least 5 minutes between measurements, the average of all three measurements will be recorded
2. The study investigator will reduce the dose of study drug back to previously tolerated dosing
3. If hypotension or bradycardia develop after initiation prior to uptitration, study drug will be stopped

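### Exercise tests are read from named files with no stated rule for placing the anaerobic threshold, which leaves the threshold-based secondary endpoints open to functional unblinding despite formal masking

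*Combined protocol and SAP*

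**What the plan says.** **Who reads, and from what.** Section C.3 states: "The stress test data will be interpreted at Children's Medical Center by a study investigator and will contain the patient's name". The same section says that the link between name and study ID "will only be accessible to the PI, study investigators and research coordinators".

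**Masking.** Section C.5.1 says of the primary and most secondary endpoints that they "will be measured by the study investigator, who will be unaware of each subject's treatment group assignment". It does not list which secondary endpoints are meant. The pharmacy determines the sequence, and "No one else including subjects, their families, and primary care providers will be informed of the subject's treatment assignment".

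**What the test shows.** Section C.7.3 draws peak heart rate, peak VO2, ventilatory efficiency and submaximal performance from one exercise test, done at Visits 1, 6, 7 and 12. The hypothesis of Secondary Aim 1 is "Carvedilol will decrease peak heart rate".

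**What depends on the threshold.** VO2 at anaerobic threshold leads Secondary Aim 2, with watts and RER at threshold behind it. VE/VCO2 at threshold leads Secondary Aim 3. Section B.3.3 defines the threshold only as a physiological concept. Sections B.3.4, C.7.3 and C.8.1 add no algorithm, reading rule, second reader, coded file or reading order.

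**Other duties of the role.** For bradycardia or hypotension, section C.7.4 says "The study investigator will reduce the dose of study drug back to previously tolerated dosing". Section C.7.6 lets a study investigator, among others, screen for side effects.

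**The concern.** Keeping the allocation at the pharmacy prevents disclosure. It does not prevent inference. A name on the file lets the reader set one participant's tests side by side and connect them with what was seen in clinic. In a two-period crossover, inferring the treatment in one period gives the other as well.

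This matters most where the reader has latitude in producing the number. With no stated method, the placement of the threshold is left to whoever reads the test. A reader who suspects the sequence could, without intending it, place the threshold differently in the two periods. A shift common to both periods cancels in the treatment contrast, but one that follows the suspected treatment does not. The lead measures of two of the four secondary aims would carry that bias into a result that the Overview says will inform a larger multicenter trial.

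**Working it through.** **1. The plan's own figure.** Section C.8.2 gives the only power calculation, for peak VO2: SD 6.3, correlation 0.8, difference 2.6 ml/kg/min, two-sided alpha 0.05, n=20.

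- SD of change = 6.3 × √(2 × (1 − 0.8)) = 3.98, as stated.
- Paired t-test power at n=20 (noncentral t) = 79.1%, or 78.9% with n − 2 degrees of freedom, against the stated 80%.

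The figure reproduces. The masking point neither depends on it nor changes it. It only supplies the n and the type of test for step 4.

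**2. The sections side by side.**

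- C.5.1 rules out telling the reader the allocation. It also bars clinical investigators from seeing pooled or per-arm outcomes before the end. Neither provision covers reading one participant's tests together.
- C.3 makes that linkage possible, through the name on the file and access to the ID link.
- C.7.3 and Secondary Aim 1 supply a cue, peak heart rate. That the reader sees it is an inference: the test produces it and no section hides it.
- C.7.4 and C.7.6 give the study-investigator role knowledge of dose reductions and possibly of side effects. No section says that the reader is a different person, and none says that it is the same one.
- Exposed: VO2, watts, RER and VE/VCO2 at threshold. Not exposed in this way: peak VO2, and the VE/VCO2 slope, which section B.3.4 fits over the whole test.

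**3. How informative could heart rate be?** The documents give no size for the fall in peak heart rate, so these inputs are assumptions. If the within-patient difference between the two end-of-period tests is normal with mean fall D and standard deviation s, a reader who calls the lower value carvedilol is right with probability Φ(D/s).

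| Fall D (bpm) | s = 8 | s = 10 | s = 15 |
|---|---|---|---|
| 5 | 73.4% | 69.1% | 63.1% |
| 10 | 89.4% | 84.1% | 74.8% |
| 15 | 97.0% | 93.3% | 84.1% |
| 20 | 99.4% | 97.7% | 90.9% |

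Guessing alone would give 50%.

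**4. What would a reader shift do?** Let b be the average net shift in the paired carvedilol-minus-placebo difference, in SDs of that difference, when there is no true effect. The chance of two-sided p < 0.05 is that of a paired t-test with noncentrality b√n.

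| Net shift b | n = 20 | n = 30 |
|---|---|---|
| 0 | 5% | 5% |
| 0.10 | 7.1% | 8.3% |
| 0.25 | 18.6% | 26.3% |
| 0.50 | 56.5% | 75.4% |

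The shift is net because wrong guesses offset right ones. A reader who moves the difference by c towards the believed treatment, and is right with probability p, produces b = c(2p − 1). At p = 0.841 the factor is 2 × 0.841 − 1 = 0.682; at p = 0.631 it is 0.262. The paired t-test stands in for the mixed model of section C.8.1, which also adjusts for pre-phase values, so these rates are approximate. The direction of any bias is unknown.

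**The case against.** The case on the other side is substantial, and most of it limits the point rather than removing it.

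- **Masking is stated.** A name discloses no allocation, and the sentence in C.3 is about confidentiality. A reader might infer that masking of the reader is merely nominal. C.5.1 does not support that: "The primary endpoint and most of the secondary endpoints will be measured by the study investigator", who is declared unaware of assignment. What remains is possible inference.
- **Two links are inferred.** The documents do not say that heart rate is in front of the reader when the threshold is placed, nor that the threshold is set by judgement; it could come from software. The supported statement is that no method is specified.
- **Overlap of roles is possible, not stated.** C.3 speaks of study investigators in the plural, and C.7.6 allows several roles to screen. Dose reductions apply to masked drug, placebo included, so they hint at treatment without revealing it.
- **The cue may be weak.** Section B.3.2 allows that carvedilol may not worsen chronotropic incompetence, although Secondary Aim 1 states a fall plainly.
- **The primary endpoint.** A reader might also infer that peak VO2 is at risk, because C.6.3 says the family, "primary care provider, and cardiologist will receive extensive information regarding" the subject's cardiac status, so that Visit 6 results could reveal the sequence before Visit 12. That section gives no timing and does not mention exercise results. The route then needs a correct guess and a change of effort. The documents do not support it.
- **Heart rate is a cue with any beta-blocker.** This is true, and coding the files will not mask the clinic. It does break the link to the person who places the threshold.

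**Conclusion.** The point holds in limited form. The assessor is formally masked, but named files, a treatment-related signal in the same test, no stated separation of reader and dose-adjuster, and no specified threshold method together leave four secondary measures open to functional unblinding. They include the lead measures of Secondary Aims 2 and 3.

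The size cannot be found from the documents. The identification rates rest on assumed falls of 5 to 20 bpm and within-patient SDs of 8 to 15 bpm. The false-positive rates rest on assumed net shifts of 0.10 to 0.50 SD. They show that a modest treatment-related shift would matter at this sample size; they do not show that any shift will occur. The sample size needs no change. With only secondary measures exposed in a preliminary study, this is a cheap improvement rather than a flaw that undermines the trial.

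**What to change.** For the study read of the threshold endpoints only:

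1. Write one rule for locating the anaerobic threshold into section C.7.3, before any study read is done.
2. Export the gas-exchange data under a code, with name, visit, date and heart rate removed.
3. After a participant's Visit 12, have an existing investigator place the threshold on all four tests in random order by that rule. Preferably this is someone who did not do that participant's identified clinical read or dose adjustments.
4. Keep the identified read, as now, for clinical safety.
5. State in C.5.1 which secondary endpoints are covered by the masked read.

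**Cost.** No new participants, tests or readers are needed. Each test is handled twice, and study threshold values are not available until after Visit 12. If staffing means that the same person does both reads, some residual unblinding remains, because that reader may remember the identified test.

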### **C.3.1. Gender and Minority Inclusion**

Based on current rosters of patients with Fontan circulation at Children's Medical Center of Dallas, it is estimated that 50% of patients will be female and 15-35% of the patients will be of minority race/ethnicity. Race, gender and other patient characteristics will not be considered when targeting enrollment.

### **C.4 Screening Phase**

A screening exercise test and safety laboratories will be performed. If the study participant meets inclusion criteria for the treatment phase ( $RER > 1.0$  at maximal

exercise test) and does not meet exclusion criteria for the treatment phase (serum albumin <2.0g/dL, hemoglobin <7gm/dL or hemoglobin >18gm/dL, AST and/or ALT > 3 times upper limit of normal, BNP>300pg/ml, or serum creatinine greater than 2.0mg/dL) s/he enter the treatment phase of the study within 14 days from screening testing. Study participation will be terminated for all subjects who do not enter the treatment phase of the study.

## **C.5 Treatment Phase**

### **C.5.1 Masking of Treatment Group Assignment**

The primary endpoint and most of the secondary endpoints will be measured by the study investigator, who will be unaware of each subject's treatment group assignment. Randomization to treatment arm (carvedilol first versus placebo first) will be determined by Children's Medical Center investigational drug pharmacy.

No one else including subjects, their families, and primary care providers will be informed of the subject's treatment assignment.

The Data Safety and Monitoring Board (DSMB) will determine their preference for receipt of blinded or unblinded trial results prior to the interim look. No clinical investigators will review trial outcomes, by arm or in aggregate, until the end of the trial.

### **C.5.2 Randomization**

After eligibility has been confirmed as described above in C.2.1.a-d and the trial consent has been signed, subjects will be randomly assigned in a 1:1 ratio to receive carvedilol or placebo first using randomly permuted blocks. All eligibility criteria must be confirmed, and written informed consent obtained, before randomization.

Randomization will be accomplished by Children's Medical Center of Dallas Investigation Drug Pharmacy.

### **C.5.3 Study Drugs**

#### **C.5.3.1 Uptitration Period**

After the baseline clinical evaluation, all subjects will be entered into the uptitration period, during which they will receive carvedilol or placebo in addition to their usual medications. The goal of the uptitration period is to reach the effective dose (defined below) that will then be continued throughout the maintenance phase. Based upon the subject's body weight, the pharmacist will determine the appropriate initial dose of carvedilol. Starting doses and the up-titration are shown in Table 1. Dose ranges are provided but actual doses will be rounded up or down according to the available pill sizes (3.125mg increments). Each drug will be administered twice a day, at about the same time of day.

**Table 1. Uptitration Schedule (all dose ranges in mg/kg/dose)**

Weight Classification		Initial Dose	Uptitration 1	Uptitration 2
20-<30kg	Absolute Dose	1.56 mg	3.125 mg	6.25 mg
	Dose Range	(0.06-0.08)	(0.10-0.16)	(0.20-0.32)
30kg-<40kg	Absolute Dose	3.125 mg	6.25 mg	9.375mg
	Dose Range	(0.08-0.10)	(0.16-0.2)	(0.23-0.31)
40kg-60kg	Absolute Dose	3.125 mg	6.25 mg	12.5 mg
	Dose Range	(0.05-0.08)	(0.10-0.16)	(0.20-0.32)
>40kg	Absolute Dose	6.25 mg	12.5 mg	25 mg

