#### **C.6.2.b Protection Against Risks**

To minimize the potential risks listed in Section C.6.1 the following steps will be taken:

1. The starting doses of carvedilol will be low and will be up-titrated carefully (see Table 1).
2. Subjects with known renal dysfunction will be excluded from the study.
3. Blood draws, to the extent possible, will be performed after the application of a topical anesthetic cream.
4. Serum creatinine, BNP, hemoglobin, hematocrit, AST and ALT will be measured as during the screening phase. Serum creatinine, BNP, AST and ALT will be measured during the treatment phase (Table 5).
5. Pregnancy or a planned pregnancy during the trial are exclusion criteria. A urine pregnancy test will be obtained during the screening phase. A statement regarding the potential risk of one of the study drugs will be given to female subjects of child-bearing potential and to the parents of female subjects less than 18 years of age. They will be asked questions about the subject's sexual activity. In addition, this risk is listed in the consent and the assent. Written documentation of birth control measures will be required for female subjects who are sexually active.
6. The study sponsor will pay for all testing that is not part of routine care.

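### Table 1 gives participants above 40 kg and up to 60 kg two dosing rows whose doses differ two-fold at every step; the last row was probably meant to start above 60 kg

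*Combined protocol and SAP*

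**What the plan says.** C.5.3.1 makes body weight the selector: "the pharmacist will determine the appropriate initial dose of carvedilol", with the starting doses and titration steps taken from Table 1. Each dose is given twice a day.

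The three upper weight rows of Table 1 are:

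- "30kg-<40kg Absolute Dose 3.125 mg 6.25 mg 9.375mg"
- "40kg-60kg Absolute Dose 3.125 mg 6.25 mg 12.5 mg", with mg/kg ranges of "0.05-0.08) (0.10-0.16) (0.20-0.32"
- ">40kg Absolute Dose 6.25 mg 12.5 mg 25 mg", with no mg/kg range

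The table heading gives the units of the ranges: "all dose ranges in mg/kg/dose".

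Two other sections depend on the table. C.6.2.b lists as its first protection: "The starting doses of carvedilol will be low and will be up-titrated carefully (see Table 1". Under C.7.4, bradycardia or hypotension normally leads to a return to the last tolerated dose, with one exception: "If hypotension or bradycardia develop after initiation prior to uptitration, study drug will be stopped".

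**The concern.** The two highest weight bands overlap. Every weight above 40 kg and up to 60 kg satisfies both labels, and the two rows prescribe different doses. The rounding rule in C.5.3.1 concerns pill size and does not choose between rows. No other section does so either.

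Three things depend on which row is used.

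- **Starting dose.** Choosing the last row doubles the first dose and each later dose for this weight band. That bears directly on the protection claimed in C.6.2.b.
- **Handling of adverse events.** In the 40–60 kg row, 6.25 mg is the first up-titration step, so bradycardia or hypotension at that dose leads back to 3.125 mg. In the last row, 6.25 mg is the starting dose, so the same event at the same dose means study drug is stopped.
- **Recording of deviations.** C.5.3.3 requires departures from the dosing schedule to be noted. With two applicable rows, neither dose in this band can be identified as a departure.

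**Working it through.** **Inputs.** All come from Table 1: the weight limits and absolute doses of each row, and the printed mg/kg ranges.

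**Step 1: reproduce the printed ranges for the 40–60 kg row.** Formula: absolute dose ÷ weight, at 60 kg for the low end and 40 kg for the high end.

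| Step | At 60 kg | At 40 kg | Printed range |
|---|---|---|---|
| Initial | 3.125/60 = 0.052 | 3.125/40 = 0.078 | 0.05–0.08 |
| Uptitration 1 | 6.25/60 = 0.104 | 6.25/40 = 0.156 | 0.10–0.16 |
| Uptitration 2 | 12.5/60 = 0.208 | 12.5/40 = 0.3125 | 0.20–0.32 |

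The printed figures are reproduced to within 0.01 mg/kg. The same holds for the two lighter bands; the largest gap there is 1.56/30 = 0.052 against a printed 0.06. The low ends of the 40–60 kg row come from dividing by 60 kg, so that row was built to run up to 60 kg.

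**Step 2: ratio of the two overlapping rows.** 6.25/3.125 = 2; 12.5/6.25 = 2; 25/12.5 = 2.

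**Step 3: mg/kg/dose in the overlap, 41 to 60 kg.**

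| Step | 40–60 kg row | Over-40 kg row |
|---|---|---|
| Initial | 3.125/60 to 3.125/41 = 0.052–0.076 | 6.25/60 to 6.25/41 = 0.104–0.152 |
| Uptitration 1 | 6.25/60 to 6.25/41 = 0.104–0.152 | 12.5/60 to 12.5/41 = 0.208–0.305 |
| Uptitration 2 | 12.5/60 to 12.5/41 = 0.208–0.305 | 25/60 to 25/41 = 0.417–0.610 |

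At 50 kg the choice is 0.0625/0.125/0.25 or 0.125/0.25/0.50 mg/kg/dose. Even at 60 kg, where mg/kg is lowest, the last row's doses (0.104, 0.208, 0.417) lie above the top of the ranges printed for the 40–60 kg row (0.08, 0.16, 0.32).

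**Step 4: try the likely correction.** If the last row starts above 60 kg, the bands are 20–<30, 30–<40, 40–60 and >60 kg, with no gap and no overlap. The final dose then steps from 12.5/60 = 0.21 mg/kg/dose at 60 kg to 25/61 = 0.41 at 61 kg. It comes down to 0.32 at 25/0.32 = 78 kg.

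**The case against.** The strongest reply is that the table explains itself. If the last row governed the overlap, the 40–60 kg row would apply only at exactly 40 kg and its printed ranges would have no purpose. A start above 60 kg is the only reading that continues the bands, and a pharmacist could see this. The literal text also does not select the higher dose, because both rows apply. This is fair as to intent, and it is why the correction is described as probable. It does not remove the need to correct the rule by which drug is dispensed.

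Other points on that side, and what stands of each:

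- *The defect rests on one digit in a table extracted from PDF.* A misread cannot be excluded, although the rest of the table reads coherently. The source table should be checked first.
- *The mg/kg ranges are not safety caps.* Correct. They are dose divided by weight. They serve here as evidence of which row was meant for 40–60 kg, not as evidence of toxicity.
- *Safeguards exist.* A single pharmacy dispenses, vital signs are taken at the titration visits, and dose-reduction rules apply. These limit harm once a dose has been given, but they do not choose the row.
- *The step at 60–61 kg arises only after an assumed correction, and the protocol does not require continuity across bands.* True. It is a question to confirm while the cell is being corrected, not a second error.

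**Conclusion.** The concern holds. As printed, Table 1 assigns two rows to every weight above 40 kg and up to 60 kg, with a two-fold difference at each of the three steps, and the document does not resolve the choice. That the last row should start above 60 kg is an inference from the printed ranges and the sequence of bands.

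The conclusion assumes that the extracted text matches the source table. The document gives no toxicity threshold and no weight distribution, so neither the harm nor the number of participants affected can be quantified. The power calculation is unaffected, and no bias between carvedilol and placebo is shown or claimed. This should be fixed because it is an error in the operative dosing rule.

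**What to change.** 1. Check the source table. If the label there already starts above 60 kg, no amendment is needed.
2. Otherwise amend the last row's weight label so that each weight maps to exactly one row, probably above 60 kg, with the cut-off confirmed by the sponsor's clinicians and the pharmacy.
3. In the same exchange, confirm that the step from about 0.21 to 0.41 mg/kg/dose just above 60 kg is intended.
4. Check that the pharmacy's dosing worksheet uses the same bands.

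The cost is one table cell changed by protocol amendment and one check of the worksheet.
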